Number of Subjects:	The sample size will be approximately 400 patients, 200 in the retrospective STANDARD THERAPY group and 200 in the prospective CHANGE IN PRACTICE group.		
Study Population:	The study population consists of adult post-surgical patients who have undergone thoracic, aortic or upper abdominal surgery who are at high risk for PPCs.		
Inclusion/Exclusion Criteria:	
Inclusion Criteria:
 
Patients who meet all of the following criteria will be included in the study:
 
• Age \geq 18 years• Post-thoracic, -upper abdominal or -aortic surgery• Open surgical procedure• Incision at or above the umbilicus• High risk defined by:
• Documented ASA class \geq 3 
OR
 
• Documented ASA class 2 AND One or more of the following:
• Current smoker or smoking history within past 6 months• History of COPD• Documented obesity and/or BMI \geq 30 kg/m²• Age \geq 75 
Exclusion Criteria:
 
Patients who meet any of the following criteria will be excluded (or will be exited) from the study:
 
• Contraindication to Continuous High Frequency Oscillation (CHFO) therapy (e.g. untreated tension pneumothorax)• Minimally invasive, or “... scopic” procedure.• Spinal surgery involving a posterior approach• Surgery for organ transplant• Chronic invasive positive pressure ventilation (PPV)		

Statistical Methods:	
Descriptive summary statistics will be provided for demographics, the primary and secondary endpoints. Continuous data will be summarized with N, mean, median, standard deviation, min, and max. Categorical data will be summarized with the number and percent of patients in each category. Time to event data (ex. Time to readmission) will be summarized with methods appropriate for survival data including a Kaplan-Meier plot.
 
Ninety-five percent (95%) confidence interval will be computed for the primary endpoint, the incidence of significant postoperative pulmonary complications. Incidence rates for various demographic subsets, surgery types, and different population subsets may be presented as outlined in the statistical analysis plan document, to be published prior to study completion. Stage I and Stage II incident rates will be compared for the purpose of identifying any statistical associations that can be attributed to use of The MetaNeb® System.
		

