1.0 Introduction

1.1 Background and Significance

Post-operative pulmonary complications (PPC) are associated with significant excess morbidity, mortality and healthcare expenditure. The incidence of “important” PPCs, across all surgeries, is approximately 2-5% in the general surgical population. There are factors, however, that place certain patients, and patients with certain procedures, at considerably higher risk for PPCs. One of the key factors in development of PPCs is the type of surgery. Following upper abdominal and thoracic surgery, pulmonary complications are the most common surgical complications. Other risk factors include advanced age, American Society of Anesthesiologists (ASA) physical status classification score ≥ 2 , functional dependency, congestive heart failure and chronic obstructive pulmonary disease. Of these, ASA score ≥ 2 and functional dependency have consistently been associated with a higher rate of significant PPCs such as post-operative respiratory failure (PRF). PRF requiring prolonged mechanical ventilation (MV) or re-intubation accounts for the majority of poor outcomes and high economic costs.^[1-4] Other risk factors that have been associated with increased risk of PPCs include history of COPD, smoking history and BMI $\geq 30 \text{ kg/m}^2$.^[1-5]

Although PPCs are an incompletely understood multifactorial syndrome, atelectasis is recognized as a critical component.^[6] Evidence has shown that atelectasis is a common precursor and concomitant feature of PPCs. Nearly all patients undergoing major surgery experience some degree of transitory, clinically unimportant atelectasis, most of these patients do not require aggressive therapy. There is, however, a more urgent need to treat atelectasis in subpopulations of high-risk individuals, in order to prevent more serious complications including progression to PRF.^[7]

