The secondary endpoints as listed in section 3.3 will be summarized with descriptive summary statistics appropriate for continuous or categorical data, depending on the outcome being summarized:

1. Requirement for invasive mechanical ventilation for more than 48 hours.
2. Requirement for respiratory support for more than 48 hours
3. Length of ICU stay (ILOS)
4. Length of hospital stay (HLOS)
5. Time on mechanical ventilation
6. Readmission to ICU
7. Readmission to hospital

Hill-Rom®	Evaluation of a practice change to include The MetaNeb® System to reduce postoperative pulmonary complications	Page 23 of 31
CBI	8 September 2016	Rev C

Stage I and Stage II results will be compared for the purpose of identifying any statistical associations that can be attributed to use of The MetaNeb® System.

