### **3 STUDY DESIGN**

This is a non-randomized facility level pre-post intervention study conducted in two stages for the primary purpose of evaluating the effect of The MetaNeb® System on postoperative pulmonary complications in high risk patients undergoing thoracic and abdominal surgeries. The study will be conducted in two to four (2-4) tertiary academic medical facilities in the US that have not previously used The MetaNeb® System in post-thoracic, post-aortic, or post-upper abdominal surgery patients. After assessing outcomes during a baseline period, therapy with The MetaNeb® System will be introduced and incorporated into the respiratory care treatment regimens and outcomes will be assessed after the change in practice.

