## 5 SAMPLE SIZE JUSTIFICATION

No formal sample size determination was performed for this study.

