### **6.1.3 Demographic and Baseline Characteristics**

Demographic and baseline data will be summarized separately for Stage I and II. Demographic data including age (years), age category (<35, 35-54, 55-64, ≥65), gender, race, ASA score, height, weight, BMI, and documented obesity (BMI≥30kg/m^2) will be summarized.

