### **6.1.6 Pre-Surgery Respiratory Status**

Pre-surgery status of invasive mechanical ventilation, non-invasive mechanical ventilation, CPAP, and supplemental oxygen will be tabulated.

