### **6.3 Analysis Methods – Primary and Secondary Endpoints**

#### **Primary Endpoint— Proportion of subjects who have a postoperative pulmonary complication**

The proportion of subjects who have a PPC within 7 days of post-surgery hospital admission will be presented with 95% confidence intervals.

Incidence of each of the 4 components that contribute to the primary endpoints, will also be presented.

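### Recorded risk factors for postoperative pulmonary complications enter no between-stage analysis, leaving the non-randomised stage comparison open to confounding by measured patient risk

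*SAP*

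**What the plan says.** **Design and purpose.** SAP section 3 states: "This is a non-randomized facility level pre-post intervention study conducted in two stages". Protocol 3.5.2 adds: "Stage I and Stage II results will be compared for the purpose of identifying any statistical associations that can be attributed to use" of the device, and the Synopsis says the same of the incidence rates. Neither gives a method for the comparison.

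**Primary analysis.** SAP 6.3 provides "The proportion of subjects who have a PPC within 7 days of post-surgery hospital admission will be presented with 95% confidence intervals", together with the incidence of each of the four components. It contains no regression, stratification, standardisation, matching or propensity method, and no named between-stage estimate or test.

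**Risk factors.** Protocol 1.1 treats type of surgery, advanced age and ASA class as risk factors, and continues: "Other risk factors that have been associated with increased risk of PPCs include history of COPD, smoking history and BMI" of 30 or more. Protocol 3.4.1 records age, ASA score, BMI, COPD, surgery type and pre-surgery respiratory status, and Protocol 3.1.2 has baseline data collected in both stages.

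**Their use.** SAP 6.1.3: "Demographic and baseline data will be summarized separately for Stage I and II". SAP 6.1.5 tabulates pulmonary history, including COPD. SAP 6.1.6: "Pre-surgery status of invasive mechanical ventilation, non-invasive mechanical ventilation, CPAP, and supplemental oxygen will be tabulated". Protocol 3.5.2 also plans descriptive PPC incidence by demographic subset and surgery type and leaves the choice of subsets to the SAP, which names none.

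**The concern.** In a pre-post comparison, any difference in patient mix between the stages becomes part of the PPC difference, in either direction. Eligibility does not remove the variation: it admits everyone from ASA 2 with one added risk factor up to any ASA class of 3 or more.

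The two stages also fill their primary populations differently. Stage I is a random sample of charts under a requested consent waiver (Protocol 3.1.2 and 5.1). Stage II requires informed consent (Protocol 5.1), and SAP 6.2 removes Stage II patients who did not receive the device. Both Stage II filters could be related to how sick a patient is. Drawing Stage I from the preceding year addresses season and recency of practice, not patient risk.

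At stake is whether a shift in measured risk, which the trial's own data could largely account for, is read as a device effect or hides one.

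**Working it through.** The plan has no power, effect size or adjusted estimate to reproduce (SAP section 5: "No formal sample size determination was performed for this study").

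**Inputs from the documents**
- About 200 patients per stage (Protocol Synopsis).
- Two-sided 5% tests (SAP section 6).
- PPC incidence of 5% to 15% in published work (Protocol 3.5.1).

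**Assumed inputs**
- A low-risk stratum at 5% and a high-risk stratum at 15%, using the ends of that range.
- The high-risk share in each stage.
- No device effect.

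**1. Crude rates.** Rate = 0.05 + 0.10 × high-risk share.
- Shares 70% v 50%: 12.0% v 10.0%, ratio 0.10/0.12 = 0.83, a false 17% relative reduction.
- Shares 75% v 45%: 12.5% v 9.5%, ratio 0.76, a false 24% reduction.

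**2. False-positive rate.** SE = √[p₁(1−p₁)/200 + p₂(1−p₂)/200]. Rejection = Φ(d/SE − 1.96) + Φ(−d/SE − 1.96).
- 12.0% v 10.0%: SE = √[(0.1056 + 0.0900)/200] = 0.0313; d/SE = 0.02/0.0313 = 0.640; rejection 0.093 + 0.005 = 9.8%.
- 12.5% v 9.5%: SE = 0.0313; d/SE = 0.960; rejection 0.159 + 0.002 = 16.0%.

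**3. Sensitivity to the strata.** With strata of 10% and 15%, rate = 0.10 + 0.05 × share.
- 70% v 50%: 13.5% v 12.5%, SE 0.0336, d/SE 0.297, rejection about 6%.
- 75% v 45%: 13.75% v 12.25%, SE 0.0336, d/SE 0.446, rejection about 7%.

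**4. A second model.** Simulation of 2,000 trials per scenario, 200 per stage, one continuous risk score with odds ratio 1.5 to 2.5 per SD, Stage II at lower risk, no device effect:

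| Baseline PPC | Shift | Crude difference (points) | Crude false positives |
|---|---|---|---|
| 15% | 0.5 SD | −2.4 to −4.5 | 11–27% |
| 15% | 0.25 SD | −1.3 to −2.5 | 7–12% |
| 5% | 0.5 SD | −0.9 to −1.8 | 6–13% |

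After adjustment the bias was about zero and the false-positive rate about 4–5%. For scale, the 95% half-width of a crude difference with equal rates is 1.96 × √[2p(1−p)/200]: 4.3, 5.9 and 7.0 points at 5%, 10% and 15%.

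**5. Does adjustment also buy precision?** With 60% high-risk overall, the overall rate is 11%, and the correlation between stratum and PPC is 0.10 × √[(0.60 × 0.40)/(0.11 × 0.89)] = 0.16. Taking 15% v 7.5% as an assumed effect with balanced stages, multiplying the variance by 1 − 0.16² moves power from 66.7% to 67.8%, about 1 point.

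Under imbalance, standardise to the pooled 60% share: variance = Σ wₖ² pₖ(1−pₖ)(1/n₁ₖ + 1/n₂ₖ).
- 70/50: 0.36 × 0.1275 × (1/140 + 1/100) + 0.16 × 0.0475 × (1/60 + 1/100) = 0.000990. The crude variance is 0.000978, ratio 1.01.
- 75/45: 0.36 × 0.1275 × (1/150 + 1/90) + 0.16 × 0.0475 × (1/50 + 1/110) = 0.001037. The crude variance is 0.000977, ratio 1.06.

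So the interval widens slightly in the very cases where adjustment is needed. In the simulation the adjusted-to-crude variance ratio was 0.89–0.99 with balanced stages and 0.98–1.08 with a 0.5 SD shift.

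**6. Events available.** 400 × 5% to 15% = 20 to 60 PPCs in total, or about 10 to 30 in Stage I.

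**The case against.** **SAP 6.3 contains no stage contrast to adjust.** SAP 2.1 sets a separate estimation objective for each stage, and a proportion with an interval answers each one. The rejection rates above belong to a test that the SAP never states. This is correct, and the missing contrast has to be repaired first. But the protocol commits to the comparison, so the adjustment has to be specified when the contrast is written.

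**The 5% to 15% range is not a within-cohort spread.** The protocol ties it to patient population and type of surgery across published articles, and everyone enrolled is already high-risk. This also stands: the strata are illustrative, and narrower strata shrink the effect (step 3).

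**Safeguards exist.** Eligibility criteria and sites are common to both stages, and Stage I charts are randomly selected. The ventilation-support and oxygen criteria count only need above the patient's baseline, and chronic invasive ventilation is excluded. These reduce the exposure but do not equalise ASA class, age, COPD or BMI. The protocol's subset incidences are descriptive, and the SAP does not carry them through.

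**Not all risk is recorded.** Protocol 1.1 also names smoking, functional dependency and heart failure, and none is in the listed baseline data. Adjustment for what is recorded is therefore partial.

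**Conclusion.** The point holds as a gap in pre-specification: measured patient risk is left out of the comparison on which a device attribution would rest. Under the assumed 5% and 15% strata and the two assumed imbalances, the false difference is 2 to 3 percentage points and the false-positive rate about 10% to 16% instead of 5%. Narrower strata bring it to about 6% to 7%. The direction could equally run against the device.

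A reader might infer two stronger things that the documents do not support. The first is that the comparison is confounded: there are no data on imbalance, so only exposure to confounding can be stated. The second is that adjustment would narrow the interval or raise power: with balanced stages the gain is small, and with imbalanced stages the interval may widen. The case for change rests on bias alone.

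**What to change.** Before Stage II outcomes are seen, amend the SAP as follows.

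- **SAP 6.3:** define the stage contrast as a risk difference with 95% confidence interval, standardised by g-computation from a logistic model of PPC on stage, site, surgery type, ASA class, age, COPD, BMI of 30 or more, and any pre-surgery respiratory support. Report the crude difference beside it.
- **Sparse events:** 20 to 60 PPCs are few for this list. Specify Firth-type penalisation in advance, or a propensity score for stage, which is not limited by the PPC count. Avoid a risk score fitted to Stage I, which would rest on only about 10 to 30 events.
- **SAP 6.1.3 table:** add standardised differences between stages for these variables, so that readers can see how much imbalance there was.

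The cost is SAP wording and one extra model on data already collected, with a possibly slightly wider interval. Secular trend, different ascertainment in retrospective and prospective records, and the unrecorded risk factors would remain and should be stated as limitations.

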#### **Secondary Efficacy Endpoints**

Proportions of subjects will be presented for the following endpoints:

1. Requirement for invasive mechanical ventilation beyond Hour 48 from PSHA
2. Requirement for respiratory support beyond Hour 48 from PSHA
3. Readmissions to ICU and transfers to an elevated level of care within 7 days of PSHA during the initial hospital stay
4. Readmissions to ICU and transfers to an elevated level of care during the initial hospital stay
5. Readmissions to hospital after PSHA discharge

Mean, median, and standard deviation will be presented for the following endpoints:

1. ICU Length of Stay
2. Hospital Length of Stay
3. Time on mechanical ventilation
4. Time to extubation

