Respiratory Treatments: Standard respiratory treatments including CPAP therapy (non-continuous), IPPB, Nebulizer treatments, Chest physiotherapy, and others will be

Hill-Rom®	Evaluation of a practice change to include The MetaNeb® System to reduce postoperative pulmonary complications			Page 21 of 31
	CBI	8 September 2016	Rev C	Protocol #: CR-RR2015-001

recorded for each day until discharge from the hospital, or through day seven (7) following the day of surgery, whichever occurs first. Type of therapy and the number of treatments received on each day will be recorded.

During Stage II, each MetaNeb® therapy will be documented including time and duration of therapy and adherence to defined treatment regimen

Hospital Discharge Summary: A summary including date and time of discharge along with the location to which the patient is being discharged will be completed after discharge.

ICU Admission/Discharge Summary (Day 8 – Discharge): Dates and times of all ICU admissions, or admissions to a unit for an elevated level of care, along with discharges from those units, that occur between post-surgery day 8 and discharge from the hospital, will be documented.

Discharge Respiratory Summary (Day 8 – Discharge): Dates and times of each initiation and discontinuation of mechanical ventilation that occur between post-surgery day 8 and discharge from the hospital, will be documented.

30-day Readmission: Hospital medical records for each patient will be evaluated after 30 days post discharge, to determine if any hospital readmissions had occurred.

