#### **5. Time on Mechanical Ventilation**

Time on mechanical ventilation, during the initial hospital stay, will be documented as follows:

- Time to initial extubation
- Total time on invasive mechanical ventilation - will be determined for each patient by calculating the total number of days/hours intubated and mechanically ventilated from the time of PSHA until the time of initial hospital discharge.
- Total time on non-invasive ventilation - will be determined for each patient by calculating the total number of days/hours ordered for non-invasive ventilation from the time of PSHA until the time of initial hospital discharge.

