## 6 STATISTICAL ANALYSIS METHODS

The statistical software, SAS®, will be used for all summaries and statistical analyses.

Summary statistics will be used throughout. For continuous endpoints, the summary statistics will generally include: number of subjects with data (n), mean, standard deviation (SD), median, and range (Min, Max). For categorical endpoints, the summary statistics will generally include: number of subjects randomized and dosed, number with data, and the percentage of those with data in each category.

All statistical tests will be 2-sided with a type I error rate of 5%, unless otherwise specified.

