Secondary Endpoints derivations will follow similar logic as that of the primary endpoint, when calculating incidence of PPC > 48 hours. For time to initial extubation, if extubation occurred prior to hospital admission, then time to initial extubation will be set to zero.

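### SAP 6.3 summarises time to extubation by mean, median and SD with no rule for patients still intubated at death, transfer or discharge, so the comparison of means between stages could mislead.

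*SAP*

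**What the plan says.** SAP 2.2, under Time on Mechanical Ventilation, lists "Time to initial extubation" as a sub-item, measured during the initial hospital stay. Protocol 3.3 supplies the clock. It starts at initial intubation if that came after surgery, or at post-surgical admission if the tube was in place before surgery began.

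SAP 6.3 places time to extubation in the list introduced by "Mean, median, and standard deviation will be presented for the following endpoints". SAP 6 gives the usual content of such summaries as "number of subjects with data (n), mean, standard deviation (SD), median, and range (Min, Max".

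The only derivation rule specific to this endpoint is in SAP 6.1.1: "if extubation occurred prior to hospital admission, then time to initial extubation will be set to zero".

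The Protocol Synopsis, under Statistical Methods, says: "Time to event data (ex. Time to readmission) will be summarized with methods appropriate for survival data including a Kaplan-Meier plot". Protocol 3.5.2 describes the secondary endpoints only as continuous or categorical data to be summarised descriptively. It closes by saying that Stage I and Stage II will be compared to find associations attributable to the device.

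**The concern.** Time to initial extubation is a time-to-event outcome, and the event need not occur while the patient is observed. A patient who dies on the ventilator, or is transferred or discharged still intubated, has no extubation time. The SAP gives a value to the best outcome (extubated before admission) and none to the worst.

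Without a rule, two things can happen:

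- **No value is recorded.** The patient leaves the summary, which then describes duration only among those who were extubated. Its denominator depends on the outcome and can differ between stages.
- **Death or discharge is entered as the stop time.** A failure is then counted as an extubation, and an early death counts as a fast one.

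Under the first reading, if Stage II turns some never-extubated patients into late extubations, their long times enter the Stage II mean while their Stage I counterparts contribute nothing. A benefit could then appear as slower extubation, and the opposite change could make harm appear as faster extubation.

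**Working it through.** **1. Is the gap filled elsewhere?** No.

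- The missing-time rules in SAP 6.1.1 cover a missing clock time when the stop date exists, not the absence of extubation.
- SAP 6.1.1 carries the primary-endpoint logic to secondary endpoints only for incidence beyond 48 hours.
- Protocol 3.3 defines start and end but has no censoring or death rule.

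**2. Is there a plan figure to reproduce?** No. Neither document gives an extubation figure, and SAP 5 reports no formal sample size determination. What follows illustrates direction only. It takes the first reading (no value recorded) and 200 patients per stage, as in the documents; every other input is assumed.

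**3. Illustration A.** Assume 60 patients ventilated on arrival in each stage. In Stage I, 54 are extubated with mean 30 h and 6 never. In Stage II the same 54 are unchanged, 4 of the 6 are extubated at 150 h and 2 never.

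Planned mean = sum of extubation times / number extubated. Restricted mean = (sum of extubation times + 168 × number never extubated) / all ventilated, where 168 h = 7 × 24.

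| | Stage I | Stage II |
|---|---|---|
| Sum of extubation times | 54 × 30 = 1,620 h | 1,620 + 4 × 150 = 2,220 h |
| Planned mean | 1,620/54 = 30.0 h | 2,220/58 = 38.3 h |
| Restricted mean | (1,620 + 6 × 168)/60 = 43.8 h | (2,220 + 2 × 168)/60 = 42.6 h |

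Adding the other 140 patients as zeros, the planned mean goes from 1,620/194 = 8.35 h to 2,220/198 = 11.21 h, and the restricted mean from 2,628/200 = 13.14 h to 2,556/200 = 12.78 h. The two means move in opposite directions. The median over all 200 is 0 h in both stages.

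**4. Illustration B, other assumptions.** A share of 0%, 30% or 60% is extubated before admission (time zero). The other extubated patients follow a lognormal distribution with median 8 h and log-SD 0.9, so their mean is 8 × exp(0.9²/2) = 12.0 h. In Stage I, 1%, 2% or 5% are never extubated. In Stage II, half or all of these are extubated at 120 or 240 h, and everyone else is unchanged.

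With n₁ patients extubated in Stage I at mean m, and r rescued at T hours, the Stage II mean is m₂ = (n₁m + rT)/(n₁ + r). Across the grid, m₂ exceeds m by 0.5 to 11.8 h although no patient does worse.

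Worked case: 30% zeros, 5% never extubated, half rescued at 240 h. The 190 extubated patients contribute about 1,583 h.

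- Planned mean: 1,583/190 = 8.3 h, then (1,583 + 5 × 240)/195 = 14.3 h.
- Median: 4.8 to 5.1 h. With 0% zeros it is 8.0 to 8.2 h; with 60% zeros, 0 to 0 h.
- 28-day restricted mean (672 h): (1,583 + 10 × 672)/200 = 41.5 h, then (1,583 + 1,200 + 5 × 672)/200 = 30.7 h.
- Extubated by day 28: 190/200 = 95.0%, then 195/200 = 97.5%.
- 7-day restricted mean (168 h): (1,583 + 10 × 168)/200 = 16.3 h in both stages, because rescue at 240 h falls after the horizon.

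**5. Can the rise be offset?** Yes. The fall in the other patients' mean that cancels it is (m₂ − m)(n₁ + r)/(n₁m). This is 5% to 50% with 1% never extubated, and 24% to more than 100% with 5%. Above 100%, no improvement in the others could cancel it.

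**The case against.** Three stronger readings are tempting, and the documents support none of them.

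**That never-extubated patients are certain to drop out.** No text says so. This is inferred from silence, and a site might record death or discharge as the stop time. Because n is to be reported, a shortfall might also be visible. This stands: the supportable statement is that handling is unspecified. Neither way of filling the gap gives a sound mean.

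**That a device which rescues patients would look harmful.** The reversal concerns the mean, with all other patients held equal. The median, also planned, hardly moves, and faster extubation in others can offset the effect. This stands, so the word is could, not would.

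**That the SAP contradicts the protocol.** The synopsis gives readmission, not extubation, as its example, and Protocol 3.5.2 allows descriptive summaries for secondary endpoints, which SAP 6.3 follows. This also stands. What remains is that the synopsis calls for survival methods for time-to-event data and the SAP does not apply them here.

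The consequence is also limited. This is one sub-item of a descriptive secondary endpoint with no named test. Patients still ventilated beyond 24 or 48 hours count in the primary endpoint and the beyond-48-hour proportion, and total invasive ventilation time is calculated for each patient. Chronic invasive ventilation is an exclusion, which removes one group of long-term ventilated patients. These facts reduce the damage but do not make the extubation summary itself interpretable.

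**Conclusion.** The point holds as a gap with a definite better method, and should be corrected. As written, the SAP has no valid value for patients who die, are transferred or are discharged while intubated, and the mean time to extubation could mislead the comparison of stages.

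The size is unknown. The two illustrations show that the direction does not depend on one example, but each rests on assumed numbers never extubated, assumed rescue times and no change in other patients. The weight is moderate: it affects the reading of one secondary result, not the primary conclusion.

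**What to change.** In SAP 6.3, take time to extubation out of the mean, median and SD list and replace it as follows:

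- Present the cumulative incidence of initial extubation by stage, through hospital discharge, using the time origin in Protocol 3.3.
- Keep patients who die, are transferred or are discharged while intubated in the denominator as not extubated (a competing event). A Kaplan-Meier curve that censors them would treat them as still able to be extubated.
- Report the number of such patients in each stage.
- If a restricted mean is wanted, use a horizon longer than 7 days or label it supplementary, since a 7-day horizon misses later rescue.

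Ventilation start and stop times and discharge time and location are already collected to discharge (Protocol 3.1.2 and 3.4.1; for the later period, "Dates and times of each initiation and discontinuation of mechanical ventilation that occur between post-surgery day 8 and discharge from the hospital, will be documented"). Death is not explicitly listed as a collected item, so confirm that the discharge or exit form captures it.

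The cost is SAP wording, one extra table or plot and that form check. The small downside is that the endpoint is no longer a single simple mean.
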